1. INTRODUCTION

This document outlines the statistical methods to be implemented during the analyses of data collected within the scope of Medicines360, Protocol M360-L105 [A Phase 3, Multicenter, Open-Label Study of a Levonorgestrel 52 mg Intrauterine System for the Treatment of Heavy Menstrual Bleeding]. The purpose of this plan is to provide specific guidelines from which the analysis will proceed. Any deviations from these guidelines will be documented in the clinical study report (CSR). In the event where discrepancies in statistical analysis may be encountered between the Statistical Analysis Plan (SAP) and what is described in the study protocol, the SAP will take precedence.

2. STUDY OBJECTIVES

This study is being performed to evaluate the Medicines360 levonorgestrel-releasing IUS, LNG20 (commercially available in the U.S. as Liletta®). LNG20 IUS is expected to provide safe and effective treatment for heavy menstrual bleeding (HMB).

2.1 Primary Objective

The primary objective of this study is to assess the efficacy of a levonorgestrel 52 mg intrauterine system (LNG20 IUS) as a treatment for heavy menstrual bleeding.

2.2 Secondary Objectives

The secondary objectives of this study are to assess the safety, tolerability, bleeding patterns, and continuation rates of LNG20 IUS in women using LNG20 IUS for heavy menstrual bleeding.

3. STUDY DESIGN AND PLAN

This is a Phase 3, open-label, multicenter evaluation of the efficacy of a levonorgestrel 52 mg intrauterine system (LNG20 IUS) for the treatment of heavy menstrual bleeding.

After completing screening and confirming eligibility, approximately 100 women, 18-50 years of age, will be enrolled to receive LNG20 IUS. This study will not restrict screening or enrollment based on parity, weight or body mass index (BMI). Women who do not require contraception (e.g., not heterosexually active, using permanent contraception) may be included.

Only women who are willing to forgo contraindicated confounding treatments and systemic hormones for the ascribed period prior to the screening, during the Screening Phase and during the Treatment Phase may be enrolled. Women who are heterosexually active must

use appropriate contraceptive methods during the Screening Phase, such as male or female permanent sterilization, be willing to use a barrier method, withdrawal (if has been using as current method prior to screening) or abstinence. No other contraceptive is required during the Treatment Phase, although subjects may choose to do so as long as contraindicated products are not used.

After written consent is obtained, the subject will undergo a Screening Phase to establish eligibility and confirm the diagnosis of HMB. At the initial screening visit (Visit 1) medical history and vital signs including height and weight will be obtained and a gynecologic exam, uterine ultrasound (unless performed within 6 months), endometrial biopsy (unless performed within 6 months), high sensitivity urine pregnancy test, gonorrhea/Chlamydia testing (unless performed in the last 30 days), Pap test (unless had documented result indicating no further follow-up during anticipated study participation) and blood tests to evaluate eligibility criteria will be performed. Women who meet entry criteria at Visit 1, exclusive of pending testing results (e.g., blood tests, endometrial biopsy, Pap test, etc.) will initiate participation in up to 3 more screening visits (Visit 2, Visit 3 and Visit 4) over approximately 90 days to establish the diagnosis of HMB based on menstrual blood loss (MBL) of ≥ 80 mL/cycle in at least 2 of 3 cycles as assessed by the alkaline hematin (AH) method.

The participant is expected to have an blood sample drawn for AH assay sample within 21 days after the last day of the feminine hygiene collection (last day of menses for Screening and after the 28-Day collection interval for Treatment Phase Cycle 3 and Cycle 6). All collected feminine hygiene products and the AH blood sample will be sent to the analysis lab within a couple of business days of the visit.

The subject will be provided specific brands of feminine hygiene products and trained to complete a daily bleeding diary. Any subject for whom a pending test result from Visit 1 is reported with an exclusionary result will be discontinued from screening (screen failure).

The diagnosis of HMB will be established in the 2-3 cycles of the screening phase.

A Screening Cycle may be repeated under the following conditions:

- If a subject indicates she was unable to collect all used feminine hygiene products during a menses and, in the opinion of the Investigator, the discarded products contained a substantial volume of blood, that cycle collection may be discarded and the cycle collection repeated
- If a subject indicates she used non-study feminine hygiene products and, in the opinion of the Investigator, these products contained a substantial volume of the blood to be assayed, then that cycle collection may be discarded and the cycle collection repeated

- If subject indicates that the first cycle had significantly less bleeding than her usual cycle, then that cycle collection may be discarded and the cycle collection repeated (first cycle only)
- Only one screening cycle may be repeated. Any screening cycle collection that is assayed cannot be repeated

Due to the COVID-19 pandemic local/state public health officials, University or Hospital leadership, and Institutional Review Boards may have required subject contact changes that impacted some study data collection. Starting in March 2020, subjects were allowed up to two consecutive cycle collections to be delayed during the screening phase for the following reasons:

- 1) A subject is not permitted to have an in person visit because of a health policy implanted by the site related to COVID-19
- 2) A subject does not feel comfortable coming into the clinic during the pandemic.

The Screening Phase MBL is the MBL averaged over all cycles measured during the Screening Phase. Each Screening Phase visit will include a high sensitivity urine pregnancy test.

Enrollment (Visit 5) will occur when the LNG20 IUS is attempted to be inserted by a study Investigator using standardized procedures and must occur within 45 days of the Screening Phase visit (i.e., Visit 3 or Visit 4) in which eligibility is established. Up to two insertion attempts will be allowed within 30 days. The study IUS will be considered inserted upon successful completion of the insertion process per the instructions for use in the Liletta USPI (Allergan and Medicines360, 2020). Visit 5 will include a high sensitivity urine pregnancy test which will be repeated if a second insertion attempt is required on a separate day. Additionally, gonorrhea/Chlamydia testing will be repeated for any women with a change in sexual partner since last tested, but IUS insertion does not require waiting for the results. The following baseline assessments will occur on the day of the initial insertion attempt and not repeated should a second attempt on a different day be needed: hemoglobin, hematocrit and ferritin testing, and a subjective assessment of menstrual bleeding using a Visual Analog Scale (VAS) questionnaire.

In the Treatment Phase subjects will continue to use only the study provided feminine hygiene products and record their bleeding on a daily diary. Feminine hygiene product collection will be limited to Cycle 3 and Cycle 6 during the Treatment Phase; no repeat collection is permitted. Study assessments will be performed at clinic visits at Treatment Phase Month 1 (Visit 6), and at the end of Cycle 3 (Visit 7) and Cycle 6 (Visit 8). Each visit will include a high sensitivity urine pregnancy test. Ferritin/hematology assessments and a subjective bleeding assessment using a VAS questionnaire will be performed at Visits 7 and 8. The IUS can be removed during the study when requested by the subject or when clinically indicated. At the end of 6 28-day cycles of use, unless medically

contraindicated, study participants may opt to keep the IUS or otherwise it will be removed.

All subjects for whom the IUS was removed will be contacted 7 to 10 days after the study exit visit to assess bleeding and cramping after removal and any IUS-related or IUS procedure-related adverse events. After completion of the Treatment Phase, all subjects with ongoing IUS-related adverse events that are not resolved or stabilized will have monthly contacts or visits, as appropriate, until the event is resolved or stabilized.

Routine safety monitoring (including clinically indicated physical exams, adverse event assessments, and vital signs) will be conducted for all subjects.

4. DETERMINATION OF SAMPLE SIZE

The sample size estimate of 100 subjects is based on results from previous studies with similar endpoints as well as the goal of a lower 95% confidence around the point estimate of the primary outcome with acceptable precision, i.e., being no more than 10% lower than the point estimate. The estimation of the required number of subjects needed to evaluate the efficacy of the LNG20 IUS is based on the following assumptions:

- The expected successful treatment rate is estimated to be 80% or higher
- The lower bound of 95% confidence interval should be within 10% from the point estimate, i.e., 70% or higher to establish the efficacy of LNG20 IUS for the treatment of HMB
- Early discontinuations due to dropouts, IUS expulsions, pregnancies and other reasons will not exceed 15%

A sample size of 80 - 85 subjects completing the Treatment Phase will provide at least 71.2% lower bound of the 95% confidence interval for an expected successful treatment rate of 80% or higher based on normal approximation. Therefore, 100 subjects using LNG20 IUS with an expected dropout rate of 15 - 20% will provide sufficient number of subjects, for the goal of approximately 80 - 85 subjects completing the trial.

Subjects who discontinue treatment for any reason other than a one-time study IUS replacement within two weeks of a complete or partial expulsion will not be replaced.

5. GENERAL ANALYSIS CONSIDERATIONS

5.1 Data Summaries

Summary tables, figures, and data listings will be used to report the efficacy and safety outcomes for this study. Continuous variables will be summarized with means, standard

deviations, medians, minimums, and maximums. Categorical variables will be summarized by counts and by percentage of subjects in corresponding categories. No formal statistical testing will be performed for this study for the primary and secondary analysis.

The primary outcome measure, the proportion of subjects with successful treatment defined as end of treatment MBL <80 mL and 50% or less than baseline, will be analyzed with 95% confidence interval based on normal approximation. LNG20 IUS efficacy for the treatment of HMB will be established in this study if the lower bound of the 95% confidence interval equals or exceeds 70%.

Individual subject data obtained from the case report forms (CRFs) and any derived data will be presented by subject in data listings. Listings that include derived data fields (e.g., estimates for missing adverse event onset dates) will include the original reported data and the derived value.

All forms of output described in this plan or any amendment that follows prior to any database cut-off for analyses or final database lock are considered *a priori* considerations. Any analyses performed subsequent to database cut-off or final database lock will be considered post-hoc and exploratory. Post-hoc analyses will be identified in the CSR.

All analyses and tabulations will be performed using SAS® Version 9.3 or higher. Tables, figures, and listings will be generated in RTF/DOC (MS Word-readable) and presented in PDF format. Upon completion, all SAS programs will be validated by an independent programmer. In addition, all program output will undergo a senior level statistical review. The validation process will be used to confirm that statistically valid methods have been implemented and that all data manipulations and calculations are accurate. Checks will be made to ensure accuracy, consistency with this plan, consistency within tables, and consistency between tables and corresponding data listings. Upon completion of validation and quality review procedures, all documentation will be collected and filed by the project statistician or designee.

5.2 Data Handling

5.2.1 Conventions

Confidence intervals of proportions will be presented in percentage with one decimal point.

Percentages of categorical variables will be based on available data, and denominators will generally exclude missing values.

The precision of the original measurements will be maintained in summaries and listings, when possible. Generally, means, medians and standard deviations will be presented with an increased level of precision as follows: means and medians will be presented to one more decimal place than the raw data, and the standard deviations will be presented to two more decimal places than the raw data.

Summaries of continuous variables (except MBL) that have some values recorded using approximate values (e.g. < or >) will use imputed values. The approximate values will be imputed using the closest exact value for that measurement. Listings will present the data in the original format.

The MBL reported values such as <10 mL, <5 mL, <2.5 mL etc. are indicators of the total blood volume of assay being BQL (below the quantifiable limit) and will be imputed to half values (e.g., <5 mL will be imputed to 2.5 mL) for baseline cycles as well as post-baseline cycles.

For tables where rounding is required, rounding will be done to the nearest round-off unit. For example, if the round-off unit is the ones place (i.e., integers), values \geq XX.5 will be rounded up to XX+1 while values < XX.5 will be rounded down to XX.

For frequency counts of categorical variables, categories whose counts are zero will be displayed for the sake of completeness. For example, if none of the subjects discontinue due to "lost to follow-up," this reason will be included in the table with a count of 0. Categories with zero counts will not have zero percentages displayed.

5.2.2 Unscheduled Visits

Unscheduled visits will be used in the determination of baseline value when applicable, but will otherwise only be listed in the applicable data listings.

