6.12 Unscheduled Visits

Subjects may require an evaluation at times other than the scheduled visits. An unscheduled visit should only be conducted when the subject reports problems that are related to the IUS, study safety issues or if repeat laboratory testing is required. In such circumstances, the unscheduled visit should be performed by a study clinician to review any change in medical history and perform any examination and testing as clinically indicated.

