6.16 Management of Unevaluable Testing During the Study

An unevaluable test is any test for which the sample or specimen could not produce a result.

- Screening Phase Tests:
 - Visit 2 allows for repeat of unevaluable tests
 - If the samples or specimens from Visit 2 are also unevaluable then repeat at Visit 3 – the results must be available and reviewed for eligibility prior to enrollment
- Treatment Phase Tests (including Treatment Phase Discontinuation/Early Discontinuation)
 - Unevaluable hemoglobin/hematocrit or ferritin should be repeated as soon as possible at an Unscheduled Visit

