9.9 Other Secondary Outcomes

All other secondary outcomes will be analyzed using the Safety Population unless noted otherwise.

- Percent change in hemoglobin, hematocrit and serum ferritin from baseline to mid-treatment (Visit 7), from baseline to end of treatment (Visit 8) and from mid-treatment (Visit 7) to end of treatment (Visit 8)
- Continuation rate during Treatment Phase
- Cumulative IUS continuation rates at Treatment Phase Visit 6, Visit 7 and Visit 8 will be summarized using Kaplan-Meier methods
- Adverse events

The number and percentage of subjects with each adverse event and serious adverse event will be presented by MedDRA system organ class, preferred term, and treatment group.

Summaries will also be presented by relationship to the type of IUS or IUS insertion or removal procedure and the severity of the adverse event. All adverse events will be summarized with special attention to those events that may be related to an IUS, including:

- Perforation of the uterus;
- Low abdominal pain (not classified as dysmenorrhea);
- Uterine infection (including PID); and
- Other urogenital infections
- IUS Expulsion Rates
 - Cumulative IUS expulsion rates at Treatment Phase Visit 6, Visit 7 and Visit 8 will be summarized using Kaplan-Meier methods
- IUS Safety-Related Removal Rates
 - Cumulative IUS safety-related removal rates at Treatment Phase Visit 6, Visit 7 and Visit 8 will be summarized using Kaplan-Meier methods
- Vaginal Bleeding Flow
 - Vaginal bleeding flow (none, spotting, and light, normal, or heavy flow [bleeding]) will be summarized by incidence and duration of bleeding. Vaginal bleeding is recorded on the daily diary during the Screening Phase and baseline will be considered the worst flow severity during the screening cycles.
 - Based on World Health Organization (WHO) terminology, bleeding and spotting are defined as:
 - Bleeding: any bloody vaginal discharge for which protection, such as pads is used
 - Spotting: any bloody vaginal discharge for which protection is not used (for women who use mini pads for daily protection, extra protection is not required); if spotting and bleeding occur on the same day, it is recorded as a bleeding day
 - Vaginal Bleeding Episodes
 - Based on the individual subject's daily diary of bleeding
 - A bleeding day is when sanitary protection is used

- A bleeding episode is defined as light, normal or heavy bleeding during a minimum of one day as defined by a subject's subjective assessment

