5.3 Handling of Dropouts or Missing Data

Unless otherwise specified, missing data will not be imputed. Subjects who drop out will not be replaced and all available data will be used.

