11.8 Clinical Laboratory Evaluation

11.8.1 Hemoglobin/Hematocrit/Ferritin

The percent change in hemoglobin, hematocrit and serum ferritin will be summarized using descriptive statistics:

- from baseline to mid-treatment (Visit 7)
- from baseline to end of treatment (Visit 8)
- from mid-treatment (Visit 7) to end of treatment (Visit 8)

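### SAP 5.2.2 makes repeats of failed Visit 7 or Visit 8 hemoglobin, hematocrit or ferritin samples listing-only, and no rule assigns them to the visit they replace

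*SAP*

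**What the plan says.** Protocol 6.16 defines the problem: "An unevaluable test is any test for which the sample or specimen could not produce a result". For the Treatment Phase, including early discontinuation, it gives one remedy: "Unevaluable hemoglobin/hematocrit or ferritin should be repeated as soon as possible at an Unscheduled Visit". Protocol 6.12 agrees, since the permitted reasons for an unscheduled visit end with "or if repeat laboratory testing is required".

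SAP 5.2.2 sets the rule for data from such visits: "Unscheduled visits will be used in the determination of baseline value when applicable, but will otherwise only be listed in the applicable data listings".

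The analysis concerned is in SAP 11.8.1: "The percent change in hemoglobin, hematocrit and serum ferritin will be summarized using descriptive statistics". It names three contrasts: baseline to Visit 7, baseline to Visit 8, and Visit 7 to Visit 8. Protocol 9.9 lists the same measure among the other secondary outcomes, analysed in the Safety population.

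On missing values, SAP 5.3 says: "Unless otherwise specified, missing data will not be imputed. Subjects who drop out will not be replaced and all available data will be used". SAP 1 gives the SAP precedence over the protocol where the two differ on analysis.

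**The concern.** The protocol arranges a replacement for a sample that gave no result. The SAP's rule for unscheduled visits then places that replacement in a listing and not in the summary that lacked the value. No other SAP text brings it back. The stake is avoidable loss of evaluable women from a named secondary outcome, through a general rule that seems to have been written without this case in mind.

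Timing also matters. Under SAP 5.1 only output described before database cut-off or lock counts as planned, and SAP 1 requires deviations to be documented in the study report. If nothing changes, the statistician must either leave out valid replacement values or depart from the plan.

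**Working it through.** The plan states no figure on this point, so there is none to reproduce. The check is mainly a comparison of texts.

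**Step 1: follow one failed sample.**
- The Visit 7 sample gives no result, so the scheduled value is missing (Protocol 6.16).
- A repeat is drawn at an unscheduled visit (Protocol 6.16 and 6.12).
- The repeat is post-baseline, so the baseline clause of SAP 5.2.2 does not apply and the listing-only clause does.
- SAP 11.8.1 asks for a Visit 7 value. It has no analysis window and no mapping rule, so the repeat does not qualify on the text.
- SAP 5.3 imputes nothing here, so the Visit 7 value stays missing in the summary.

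The same path holds for Visit 8.

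**Step 2: count the contrasts lost per woman.**

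| Value lost | Baseline to V7 | Baseline to V8 | V7 to V8 | Lost |
|---|---|---|---|---|
| Visit 7 only | lost | kept | lost | 2 of 3 |
| Visit 8 only | kept | lost | lost | 2 of 3 |

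The two visits are equally costly.

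**Step 3: illustrate the size.** Inputs:
- *n*, the women who would otherwise contribute. SAP 4 aims for 80 to 85 completers and about 100 enrolled. The outcome uses the Safety population, and the number with a Visit 7 sample need not equal the number of completers, so I take 80 to 100.
- *u*, the proportion of samples unevaluable at a visit. The documents do not give it; 1% to 5% is an assumption.

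Expected women losing a given visit's value = *n* × *u*. Expected women losing the Visit 7 to Visit 8 contrast = *n* × [1 − (1 − *u*)²], taking failures at the two visits as independent.

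| n | u | Lost per visit | Lost from V7 to V8 |
|---|---|---|---|
| 80 | 1% | 0.8 | 1.59 |
| 80 | 5% | 4.0 | 7.80 |
| 85 | 1% | 0.85 | 1.69 |
| 85 | 5% | 4.25 | 8.29 |
| 100 | 1% | 1.0 | 1.99 |
| 100 | 5% | 5.0 | 9.75 |

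Example: 100 × [1 − 0.95²] = 100 × 0.0975 = 9.75. The table assumes that every repeat is obtained, is evaluable and is recorded as unscheduled; where any of these fails, the loss due to SAP 5.2.2 is smaller.

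**Step 4: why an analysis window is needed.** Protocol 6.16 sets no outer limit on the repeat, and Protocol 6.9.3 already allows Visit 7 up to Day 105. Protocol 6.10 also waives the Visit 8 blood draw if a result was obtained in the prior 6 weeks. For a Visit 8 on Day 169, that covers results from Day 169 − 42 = Day 127, which is 22 days after the latest allowed Visit 7. A very late Visit 7 repeat could therefore sit close to the Visit 8 measurement.

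**The case against.** The best counter-text is the statement in SAP 5.3 that all available data will be used. It is a general sentence alongside the rule on dropouts, and it does not displace the specific listing-only rule. At most the two sentences disagree, which is itself a reason to clarify.

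The stronger practical objection is that a site might enter the repeat on the Visit 7 or Visit 8 laboratory form. Protocol 8 has sites enter laboratory values and refers quality checks to a Data Management Plan outside these documents. If the repeat carries the nominal visit label, SAP 5.2.2 might never apply. This stands: a reader might infer that the repeat is certain to be lost, but the documents do not settle it.

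Two other inferences go too far. One is that the repeat is thrown away and the woman's extra draw serves no purpose. The value is still listed, and it serves her care: Protocol 6.15 calls for clinically significant anemia to be evaluated and treated, and Protocol 7.9 can make a clinically significant finding an adverse event. The other is that using unscheduled values at baseline but not on treatment is a flaw in itself. On-treatment unscheduled visits arise from problems or repeat testing, and keeping those results out of by-visit summaries avoids selective sampling. Only a narrow exception is missing.

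**Conclusion.** The point holds as a low-severity gap. On the text, and unless the repeat is recorded under the nominal visit, a valid replacement for a failed Visit 7 or Visit 8 sample is listed but not summarised, and the woman loses two of her three contrasts. The number affected is unknown. The range of about 1 to 5 women per visit rests wholly on the assumed 1% to 5% rate and on 80 to 100 contributing women.

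A reader might infer a threat to the trial's conclusions, or bias in the hemoglobin and ferritin results. The documents support neither. The outcome is descriptive with no formal testing, the primary menstrual blood loss endpoint and its 70% criterion are untouched, and nothing in the documents links a sample's failure to the value it would have shown. The harm is some avoidable missing data.

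**What to change.** Amend SAP 5.2.2, or add the rule to 11.8.1, before database lock. The first evaluable repeat drawn because the scheduled Visit 7 or Visit 8 hemoglobin, hematocrit or ferritin sample was unevaluable (Protocol 6.16) is assigned to that visit, provided it was drawn within a pre-specified analysis window, and is flagged as a repeat in the listing. All other post-baseline unscheduled results, including repeats of abnormal values, stay listed only. The window should be chosen so that a repeat for one visit cannot stand in for the other.

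The cost is a sentence and a visit-mapping line in the programming. The downside is small: a replacement may be drawn somewhat later than the nominal visit, possibly after iron treatment has begun. The window limits this, and the flag lets a reader see which values are affected.
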